11.1.1 Inflammation and Immune Activation

Biomarkers of immunity and inflammation are elevated in HIV and higher levels are associated with adverse cardiac events and mortality. Although HAART reduces immune activation and inflammation, studies show persistent T cell activation and inflammation despite therapy. This may be related to residual HIV replication, gut mucosal injury and microbial translocation, co-infections, and homeostatic drive, which in turn may be determined by when HAART is initiated, degree of CD4 T cell restoration, age, comorbidities, and genetic background. This proposal seeks to study the importance of persistent inflammation and immune activation despite HAART and viral suppression on development of DD, its associated pathophysiologic perturbations, and its consequences on cardiac function.

11.2 Myocardial Fibrosis and Inflammation

Advances in cardiac magnetic resonance (CMR) imaging now allow for the detection of novel structural and functional characteristics that inform the pathophysiology of cardiac dysfunction. Along with assessing standard clinical and subclinical structural and functional derangements, this study will use CMR to study focal and diffuse myocardial fibrosis, and myocardial inflammation and edema in HIV+ subjects with and without DD. A sub study assessing for diffuse interstitial fibrosis in a subset of patients using T1 mapping CMR to index ECV will be conducted.

11.3 Proteomics/Metabolomics

There remains a knowledge gap about factors that predict risk beyond traditional risk factors and the mechanisms underlying the increased risk for DD and HF in HIV. Immune dysregulation with persistence of HIV DNA and the resultant inflammation have been implicated.^{48,49} While biomarker studies have been conducted in HIV, these have focused primarily on individual inflammatory biomarkers. Many nucleoside reverse transcriptase inhibitors may result in mitochondrial toxicity⁵⁰ and some protease inhibitors can induce endoplasmic reticulum stress,⁵¹ both pathways with metabolic byproducts proposed herein. The broad representation of pathways included in the proteomics and metabolomics panels enables testing of many known pathways and identification of novel mechanisms. High throughput -omics approach has identified novel markers and mechanisms in general, but has not been specifically applied to investigation of DD and HF pathogenesis in HIV. This study therefore has a strong likelihood of identifying novel molecular pathways of DD and HF pathogenesis in HIV, and aims to identify drug targets and a deeper understanding of the relationship between HIV, DD, and HF.

11.4 Left Atrial Reserve

Left atrial (LA) dysfunction is associated with development of HFpEF. In patients with prevalent HFpEF, LA dysfunction leads to pulmonary hypertension, reduced exercise capacity, and ultimately poor clinical outcomes. This protocol will use novel speckle-tracking image analysis in order to understand subclinical functional abnormalities in the LA. The passive leg raise test will determine the ability of the LA to augment its reservoir and booster function in response to

increased preload. Dynamic changes in LA strain will identify differences between HIV+/DD+, HIV+/DD-, and HIV-/DD+ subjects.

11.5 Phenomapping

DD represents the end result of multiple risk factors. Understanding this heterogeneity of DD may allow for development of targeted prevention and treatment interventions. An ideal classification would group together pathophysiologically homogeneous individuals who may behave in a similar manner. Machine learning, the process of using data to learn relationships between subjects, is ideally suited for this. Machine learning approaches can be supervised or unsupervised. Supervised learning aim to predict specific outcomes. Unsupervised learning attempts detection of the intrinsic structure within data, independent of outcomes, and is seen as an initial strategy to derive a set of features for novel classification, which can subsequently be used for supervised learning. With sophisticated tools ranging from biomarkers to imaging, “deep phenotyping” is possible to better classify heterogeneous syndromes like DD. Applying machine learning algorithms to dense phenotyping may enable detection of novel patterns in dense, multi-dimensional data obtained from patients with DD. Prior work suggests that these “phenogroups” have unique pathophysiologic profiles and outcomes.

12 PARTICIPANT SAFETY

12.1 Institutional Review Boards

All HFN sites will submit the study protocol, informed consent form, and other study documents to their IRB for approval—the approval letter for each clinical center will be stored at the CC. Any amendments to the protocol, other than minor administrative changes, must be approved by each IRB before they are implemented.

12.2 Recording and Reporting of AEs/SAEs

General collection of AEs and SAEs will not be included for this observational study, based on the assumption that this protocol is exempt from investigational new drug regulations under FDA Code of Federal Regulations (CFR) Title 21, 312.2(b). Research sites should abide by their local IRB policies and procedures and any post marketed/spontaneous reporting regulatory guidelines for any approved drugs.

13 STATISTICAL CONSIDERATIONS

13.1 Overview

A statistical analysis plan will be completed before the data are analyzed in a blinded fashion. Statistical tests with p-value <0.05 will be considered statistically significant. The trial results will be reported according to guidelines specified in the CONSORT statement. A flow diagram describing screening, recruitment, dropout, and vital status will be included in the primary manuscript. Analyses will be performed using SAS software (SAS Institute, Inc, Cary, NC).

13.2 Power Calculations and Statistical Analysis for Biomarkers

The primary statistical comparison for Aim 1a is the between group (the HIV+/DD+ and HIV+/DD- cohorts) difference in log-transformed IL-6 biomarker levels. Log-transformed IL-6 (log pg/ml) is expected to have a standard deviation of approximately 0.75.⁵² Sample sizes of 100 subjects in each group will provide 80% and 90% power to detect differences of 0.30 and 0.35 (log pg/ml), respectively. These sample size calculations were based on a two-sample t-test with a two-sided type I error of 0.05. Additionally these calculations suggest that any comparison of (properly transformed) continuous variables between the HIV+/DD- and HIV+/DD+ cohorts will have 80% and 90% power to detect differences of 0.40 and 0.46 standard deviations, respectively. Comparisons between the HIV+/DD+ or HIV+/DD- cohorts and the HIV-/DD+ cohort will have greater power due to the larger number of subjects in the HIV-/DD+ cohort. Statistical summaries will use median (25th, 75th percentiles) and mean (standard deviation) for continuous measures and frequencies (percentages) for categorical variables. Because many biomarkers are expected to be right-skewed, we will log-transform each marker or use another appropriate transformation to normalize its distribution. Unadjusted comparisons between groups will be based on t-tests after the appropriate transformations for continuous measures and chi-square tests for categorical measures. For Aim 1a, propensity scores will be the primary tool used to obtain balanced comparisons between cohorts. The propensity score is defined as the probability of having group membership (e.g. HIV+/DD+) conditional on observed covariates and is a commonly used balancing score used in observational studies.⁵³ Three different methods of propensity score adjustment will be applied. The primary analysis method will be based on inverse probability weightings. Secondary approaches will be based on full propensity score matching and doubly-robust estimation.^{54, 55} Distributional overlap and covariate balance will be assessed using the recently developed best practices for propensity score analyses.⁵⁶ The primary adjusted analysis of IL-6 levels between cohorts will be conducted at the two-sided 0.05 level.

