3 INTRODUCTION

3.1 Background and Significance

Heart failure (HF) patients have $\approx 50\%$ mortality risk within 5 year of diagnosis, underscoring the need to better understand determinants of HF risk in order to develop effective screening and prevention interventions. An emerging risk factor for HF is human immunodeficiency virus (HIV) infection. HIV-related HF was identified as a major priority by the 2015 NHLBI AIDS Working Group. Since the early reports from the 1980s, the pattern of left ventricular (LV) dysfunction in HIV has evolved. Studies in the modern anti-retroviral therapy (ART) era have demonstrated lower rates of LV systolic dysfunction¹ but strikingly higher rates of diastolic dysfunction (DD), ranging from 26-50% as compared to 6-30% in the general population.² The mean age of HIV+ subjects with DD ranged from 38-49 years,¹ which is at least a decade younger than DD onset in the general population.³ DD is associated with atrial fibrillation, HF, and mortality.⁴⁻⁶ Thus there is a concern that the next epidemic in HIV+ patients will be HF with preserved ejection fraction (HFpEF). There is an unmet need to study DD in HIV+ patients to understand why they develop more prevalent and early onset DD.

Diastolic Dysfunction and Heart Failure

Left ventricular (LV) diastolic dysfunction (DD) is frequently present in older adults, with a prevalence ranging from 6-30% depending on the methodology, definition, and population studied. DD is associated with the development of atrial fibrillation and heart failure (HF), and portends higher risk for all-cause mortality. Previous studies have shown that DD is associated with obesity, hypertension, and metabolic syndrome, conditions that are associated with elevated inflammatory cytokines and endothelial dysfunction. It is important to note that DD is not the same as diastolic heart failure or HF with preserved ejection fraction (HFpEF). DD (also known as subclinical DD or preclinical DD) is an asymptomatic pathophysiological abnormality that precedes overt, symptomatic HF. As such, it is a clear representation of ACC/AHA Stage B HF (asymptomatic cardiac structural and functional abnormalities). It is critically important to understand DD prevalence, pathogenesis, and sequelae given its association with significant morbidity and mortality.

HIV-Related Diastolic Dysfunction and Heart Failure

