6 STUDY FLOW DIAGRAM

7 STUDY POPULATION AND ELIGIBILITY CRITERIA

Study Population

Subjects who are receiving care at a site participating in the Heart Failure Clinical Research Network program, are HIV positive, have been on HAART for ≥ 6 months and are virally suppressed will be screened for participation in the study using the inclusion and exclusion criteria listed below.

Enrolled subjects will be compared to non-HIV subjects with DD (HIV-/DD+) from MESA.

MESA Longitudinal Cohort Study

MESA is an NIH-funded longitudinal cohort study that recruited 6,814 participants from 6 centers (Winston-Salem, Los Angeles, Baltimore, Chicago, New York, Minneapolis/St Paul). At enrollment during 2000-2002, all participants were aged 45-84 and free of CV disease (CVD). There has been continuous surveillance for CVD events including HF. MESA Exam 6 will enroll

3500+ participants and will be conducted from September 2016 to March 2018. MESA Exam 6 will include comprehensive echocardiography, arterial stiffness measures, and blood collection for biomarkers. There is a concurrent echocardiographic study in MESA exam 6 that has been funded (R01 HL127028, PI [name]) that will recruit 3500+ participants from 2016-17 and will form the cohort for HIV-/DD+ for the present study; the HIV study and MESA will have an identical dynamic echocardiography protocol, with a single reading center at Northwestern University for both studies.

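### HIV-/DD+ comparators from MESA Exam 6 are all about 59 or older while HIV+ subjects enter from 40; no age handling is stated for these contrasts, and their claimed greater power holds only unadjusted

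*Combined protocol and SAP*

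**What the plan says.** Section 13.2 plans 100 HIV+/DD+ and 100 HIV+/DD- subjects and bases power on an unadjusted two-sample t-test at two-sided 0.05: "Sample sizes of 100 subjects in each group will provide 80% and 90% power to detect differences of 0.30 and 0.35 (log pg/ml), respectively". It then extends the claim to the outside comparator: "Comparisons between the HIV+/DD+ or HIV+/DD- cohorts and the HIV-/DD+ cohort will have greater power due to the larger number of subjects". It gives no size for that comparator group and no adjusted power calculation.

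Section 7 takes the HIV-/DD+ group from MESA. On MESA's original recruitment it says: "At enrollment during 2000-2002, all participants were aged 45-84 and free of CV disease (CVD". Exam 6 is to enroll "3500+ participants and will be conducted from September 2016 to March 2018", and the echocardiography study within it "will recruit 3500+ participants from 2016-17 and will form the cohort for HIV-/DD+ for the present study". Section 7.1 sets a lower age limit of 40 for HIV+ subjects and no upper limit. Section 3.1 reports, from cited studies: "The mean age of HIV+ subjects with DD ranged from 38-49 years".

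Propensity scores, with inverse probability weighting as the primary method and a check of distributional overlap, are specified for Aim 1a (13.2), Aim 2a (13.4) and left atrial strain (13.7). Each of these names only HIV+ cohorts. The covariate-adjusted regression in 13.5 is also a comparison within HIV+ subjects. Aims 1c, 2b, 3a and 3b in section 4 each include a comparison with HIV-/DD+ subjects, and no method of handling age is given for any of them. Earlier MESA visits are mentioned only for phenomapping (13.3).

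**The concern.** Roughly 14 to 18 years separate MESA enrollment from Exam 6, so the comparator group has an age floor well above the HIV+ entry age. Where one group has nobody of a given age, weighting or matching cannot supply a comparison at that age, and regression can only extrapolate to it.

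The protocol itself treats age as relevant: section 11.1.1 lists it among the possible determinants of persistent inflammation. The only test in 13.2 that could apply to the MESA contrasts as written is the unadjusted t-test, and it would attribute to HIV a difference that includes the age gap. If the markers rise with age, the older comparators would pull against the hypotheses of Aims 1c, 2b and 3b, so the likelier error is to hide a real HIV excess. For example, an age effect of 0.40 SD in the comparators would cancel a true HIV difference of 0.40 SD.

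The power sentence adds to this. It suggests that the MESA contrasts are the better-powered part of the study, when a comparison at like ages is limited by how many older HIV+ subjects are enrolled.

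**Working it through.** **Inputs from the protocol.** 100 subjects per HIV+ cohort; two-sided alpha 0.05; t-test; "Log-transformed IL-6 (log pg/ml) is expected to have a standard deviation of approximately 0.75"; MESA ages and dates as above; HIV+ entry at 40 or older.

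**Assumed inputs.** The number of HIV-/DD+ subjects is not stated. Section 3.1 gives DD in older adults "with a prevalence ranging from 6-30% depending on the methodology, definition, and population studied". Applied to 3,500 this is 0.06 × 3,500 = 210 to 0.30 × 3,500 = 1,050. The age distribution of the HIV+ cohort is also not stated, so ranges are used.

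**1. The plan's own figures.** Power comes from the noncentral t distribution with noncentrality d / √(1/n₁ + 1/n₂).
- 0.30/0.75 = 0.40 SD, 100 against 100: 0.40/√0.02 = 2.83, power 80.4%.
- 0.35/0.75 = 0.467 SD: power 90.7%.

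Both reproduce the stated 80% and 90%.

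**2. Age floor at Exam 6.** Age 45 at the end of 2002, seen in September 2016: 45 + (2016.67 − 2003.0) = 58.7 years. Someone aged 45 at the start of 2000 would be 61.7 to 63.3 during Exam 6. No comparator can be younger than about 59.

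**3. The power sentence, unadjusted, all 100 HIV+ subjects, 0.40 SD.**
- Against 210: √(1/100 + 1/210) = 0.1215, noncentrality 3.29, power 90.7%.
- Against 1,050: √(1/100 + 1/1,050) = 0.1047, noncentrality 3.82, power 96.8%.

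On this basis the sentence is correct.

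**4. Power using only HIV+ subjects of about 59 or older (count assumed), all MESA DD+ subjects kept.**

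| HIV+ in range | Power at 0.40 SD, N = 210 | Power at 0.40 SD, N = 1,050 | Detectable at 80% power (N = 210; N = 1,050) |
|---|---|---|---|
| 10 | 23.3% | 24.1% | 0.91; 0.89 SD |
| 20 | 39.8% | 42.5% | 0.66; 0.63 SD |
| 30 | 53.2% | 57.9% | 0.55; 0.52 SD |
| 50 | 71.7% | 78.8% | 0.44; 0.41 SD |

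These figures ignore any precision lost to age adjustment within the range, so they are optimistic.

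**5. Break-even with 100 against 100.** Set 1/n₁ + 1/N = 1/100 + 1/100 = 0.02, so n₁ = 1/(0.02 − 1/N).
- N = 210: 1/(0.02 − 0.00476) = 65.6, about 66.
- N = 1,050: 1/(0.02 − 0.00095) = 52.5, about 53.
- N = 3,500 (every Exam 6 participant): 50.7, about 51.

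However large MESA is, at least half of the 100 HIV+ subjects must be in range.

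**6. How many might be in range.** For a normal age distribution truncated at 40, with mean 45-55 and SD 6-10 before truncation (assumed), the share aged 59 or older runs from 1% (mean 45, SD 6) to 37% (mean 55, SD 10). All of these lie below break-even.

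**The case against.** Several points on the other side stand and limit what can be said.

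- **The power sentence is not an arithmetic error.** A reader might infer that it is simply wrong. Section 13.2 rests its power on an unadjusted t-test, and on that basis step 3 confirms it. What it lacks is support for an age-comparable contrast.
- **Overlap is limited, not absent.** HIV+ subjects have no upper age limit, so some will be 59 or older. The documents do not say how many. The 38-49 figure is a range of means from other studies, and a mean of 38 cannot occur in a cohort that starts at 40.
- **Inverse probability weighting is not assigned to a MESA contrast.** One might argue that the planned weights would explode, but the plan assigns weighting only where HIV+ cohorts alone are named. The gap is that no age handling is stated, not that a bad one is.
- **The benchmark is generous.** The within-HIV comparison will also be weighted and lose precision. If weighting left an effective 70 per arm (assumed), break-even would be 1/(2/70 − 1/N), about 42 for N = 210 and 36 for N = 1,050. Weighting would cost the restricted MESA contrast something too, so the direction may well hold.
- **The central comparison is untouched.** Aim 1a lies within HIV+ subjects, and Aims 2b, 3a and 3b each also have a within-HIV contrast. Section 13.1 promises an SAP before analysis, so there is room to settle this.

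None of this provides a same-age comparator for HIV+ subjects aged 40-58 or says how their results should be read.

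**Conclusion.** The concern holds in this form. The age floor of about 59 follows from the protocol's own dates and needs no assumption, as does the absence of same-age HIV-/DD+ comparators for HIV+ subjects aged 40-58. No age handling is stated for the MESA contrasts in Aims 1c, 2b, 3a and 3b, so following the text as written gives answers in which HIV and age are mixed.

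The claim of greater power is true only for that mixed comparison. It would be going too far to conclude that an age-comparable contrast must have less power than 100 against 100. That depends on fewer than about 53-66 of the 100 HIV+ subjects being in range, which is likely under the age distributions tried but is not shown by the documents. The power figures rest on the assumed 210-1,050 comparators and the assumed counts in range; the break-even near one half of the cohort holds for any comparator size.

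**What to change.** In 13.2, delete the greater-power sentence or limit it expressly to unadjusted comparisons. In the SAP, for every HIV+ versus HIV-/DD+ comparison in Aims 1c, 2b, 3a and 3b:

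1. Make the inferential analysis an age-adjusted one within the common age range, from the youngest Exam 6 DD+ participant upward. Overlap weights are one suitable method; matching or regression within that range would also serve.
2. State power or detectable difference from the number of HIV+ subjects in that range. This count needs only ages, so it can be fixed before any outcome is examined.
3. Report the full-age-range comparison as descriptive, with the age distribution of each group beside it.

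The change is one of wording and needs no new data. Its price is scientific: conclusions about HIV-related versus non-HIV DD would apply only to older HIV+ subjects, leaving out the early-onset group that section 3.1 gives as a motivation, and the power figure would probably be less favourable. Earlier MESA visits might supply younger comparators for some blood markers, but the protocol does not establish that comparable measurements exist, and it describes the shared echocardiography protocol only for the study within Exam 6.

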13.3 Phenomapping Statistical Analysis

For machine learning analyses, quantitative phenotypic data collected at clinic visits or at study enrollment for HFN cohort, and from prior and current MESA visits, will be used. These data include clinical, demographic, medication, laboratory, electrocardiogram, echocardiogram, and CMR phenotypes. We will standardize individual variables (mean 0, SD 1) so that biomarkers with larger variances will not have a greater influence on cluster assignment. We will then use gene expression hierarchical clustering software to create an unbiased phenotype heat map (phenomap). Next, in R software, we will use statistical learning approaches to refine our phenomics analysis and algorithms by using penalized model-based clustering, principle components analysis (PCA), multinomial logistic regression with lasso penalty, and cross-validation with model fitting to determine the ideal number of phenogroups.⁵⁷⁻⁶⁶ [name] has developed a generalizable logistic regression model to define membership for each pheno-group in order to permit robust classification of subjects with minimal set of phenotypic features. His model was created using a penalized form of statistical learning, specifically multinomial logistic regression with L1 norm (lasso), which determines regression coefficients by minimizing the deviance of the model, subject to a penalty for the sum of the absolute value of the coefficients. The penalty results in inclusion of only a subset of variables into the final model. The weight of the penalty (λ) was determined using 10-fold cross-validation. Cross-validation and model fitting will be performed using the *cv.glmnet* and *glmnet* functions, respectively, in the *glmnet* package within R statistical software. Using the multinomial logistic regression with lasso approach, a limited subset of variables will be used for classifying study participants into pheno-groups. Alternate

supervised and unsupervised machine learning techniques (e.g., support vector machines, tensor factorization, and neural networks) will also be explored to determine whether they are superior to unsupervised model-based clustering approaches.

13.4 cMRI Power Calculation and Statistical Analysis

The primary statistical comparison for Aim 2a is the between group (the HIV+/DD- and HIV+/DD+ cohorts) difference in myocardial fibrosis levels. The sample sizes of 100 subjects in each cohort will provide 80% and 90% power to detect differences of 0.40 and 0.46 standard deviations, respectively. For Aim 2a, propensity scores will be the primary tool used to obtain balanced comparisons between cohorts. Three different methods of propensity score adjustment will be applied. The primary analysis method will be based on inverse probability weightings. Secondary approaches will be based on full propensity score matching and doubly-robust estimation. Assessment of distributional overlap and covariate balance will be assessed using the recently developed best practices for propensity score analyses. The primary adjusted analysis of fibrosis levels between cohorts will be conducted at that two-sided 0.05 level.

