4 OBJECTIVES AND HYPOTHESIS

Multiple domains of biomarkers (fibrosis and remodeling, arterial inflammation, hypercoagulability and oxidative stress), proteomic and metabolomics analyses, and other cardiac structural and functional changes will be harnessed to elucidate the mechanistic pathways leading to DD in HIV. Exploratory analyses will assess if DD in HIV is associated with higher wall stress and the potential microvascular dysfunction in these patients leads to subclinical myocardial necrosis.

FIGURE 1

The overarching objective of this protocol is to study the determinants, mechanisms, and consequences of DD in HIV infected individuals.

Objective 1: Understand the determinants of diastolic dysfunction

Aim 1a: To compare persistent inflammation between HIV+/DD- and HIV+/DD+ subjects.

Hypothesis: HIV+/DD+ subjects will have greater levels of pro-inflammatory cytokines (IL-6, hsCRP) than HIV+/DD- subjects despite ART and viral suppression

Aim 1b: To compare immune activation between HIV+/DD- and HIV+/DD+ subjects.

Hypothesis: HIV+/DD+ persons will have greater immune activation (sCD163; sCD14; CD14 and CD16 expression; and T cell activation and subsets: Th1, Threg, CD4+, CD8+ T cell activation) than HIV+/DD- subjects.

Aim 1c: To compare inflammation between HIV+/DD+ and HIV-/DD+ subjects.

Hypothesis: HIV+/DD+ persons will have greater inflammation (IL-6, hsCRP) than HIV-/DD+ subjects.

Aim 1d: Perform phenomics of aggregate demographic, clinical, biomarker, electrocardiogram, and imaging data to define risk factor phenotype signatures, and relate these to HIV+/DD+ vs. HIV-/DD+.

Hypothesis: Specific pheno-groups will be associated with HIV+/DD+ and will differ from HIV-/DD+.

Objective 2: Understand the mechanisms of diastolic dysfunction

Aim 2a: To compare myocardial fibrosis by magnetic resonance imaging between HIV+/DD+ and HIV+/DD- subjects.

Hypothesis: HIV+/DD+ persons will have greater fibrosis burden than HIV+/DD- persons.

Aim 2b: To identify systemic determinants of DD in HIV+ persons.

Hypothesis: HIV+/DD+ persons will have higher serum levels of biomarkers of fibrosis and remodeling, arterial inflammation, oxidative stress, and hypercoagulability than HIV+/DD- or HIV-/DD+ subjects.

Aim 2c: To study the proteomic and metabolomic profile of HIV+/DD+ subjects.

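### Read most directly, Section 13.3 chooses the number of pheno-groups by a cross-validation that cannot show whether pheno-groups exist or how many there are

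*Combined protocol and SAP*

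**What the plan says.** Section 13.3 standardizes each phenotypic variable and applies hierarchical clustering to form the phenomap. It then refines the result "by using penalized model-based clustering, principle components analysis (PCA), multinomial logistic regression with lasso penalty". How many groups there are is left to the last tool in the same list: "cross-validation with model fitting to determine the ideal number of phenogroups".

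The text next describes an existing lasso classifier whose penalty weight "was determined using 10-fold cross-validation". A further sentence begins "Cross-validation and model fitting will be performed using the" and names two R functions: cv.glmnet for the first task, glmnet for the second. With this approach, "a limited subset of variables will be used for classifying study participants into pheno-groups". Other supervised and unsupervised methods "will also be explored to determine whether they are superior to unsupervised model-based clustering approaches"; the yardstick for superiority is not given.

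The section names no index for the number of groups, no one-group option, no null reference, no stability check and no independent validation cohort. The Aim 1d hypothesis in Section 4 takes pheno-groups as given and asks how they relate to HIV+/DD+ as against HIV-/DD+. Section 13.1 promises a statistical analysis plan before analysis, but the combined document contains nothing further on this choice.

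**The concern.** The lasso needs labels before it can be fitted, and here the labels are cluster assignments made from the same variables. Any clustering cuts the variable space into regions, and a regression on those variables can relearn the cut even if the data are one continuous cloud. Subjects held out of a fold also helped to define their own labels. Good cross-validated performance therefore shows that the cut can be reproduced, not that nature made it.

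Section 13.6 is a useful contrast. There, cross-validation tests prediction of diastolic dysfunction, which is defined separately by echocardiography, so accuracy carries information.

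At stake is the interpretation of Aim 1d. Section 11.5 presents unsupervised learning as a way to find structure intrinsic to the data. The described step does not test for such structure, so slices of a continuum could be reported as distinct types of disease.

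**Working it through.** Section 13.3 gives no number of groups, accuracy or sample size, so there is no plan figure to reproduce. The check is whether the described procedure can tell groups from no groups.

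**Inputs.** From the documents: about 200 HIV+ subjects (Section 5), standardized variables, hierarchical clustering, a multinomial lasso and 10-fold cross-validation (Section 13.3). Assumed, because the documents do not give them: 40 variables; n = 100, 200 and 400; variables either independent or correlated through three continuous factors. There were eight data sets per setting.

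**Step 1: no groups present.** Each data set came from a single Gaussian population. Labels for K = 2 to 5 were made by Ward or k-means clustering. The lasso was then cross-validated on the same variables, with the penalty at minimum deviance. Mean accuracy at n = 200, with the largest-class rate in brackets:

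| K imposed | Ward, independent | k-means, independent | Ward, correlated | k-means, correlated |
|---|---|---|---|---|
| 2 | 0.80 (0.59) | 0.95 (0.58) | 0.91 (0.61) | 0.95 (0.55) |
| 3 | 0.77 (0.46) | 0.91 (0.43) | 0.85 (0.45) | 0.93 (0.38) |
| 4 | 0.72 (0.39) | 0.87 (0.41) | 0.83 (0.36) | 0.88 (0.30) |
| 5 | 0.70 (0.33) | 0.83 (0.30) | 0.80 (0.31) | 0.85 (0.28) |

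Over all three sample sizes, accuracy was 0.67–0.91 (Ward) and 0.74–0.97 (k-means), and the cross-validated share of deviance explained was 0.34–0.88. A separate simulation with n = 300, 46 variables and five factors gave 88.5%, 83.1% and 79.6% (Ward) and 95.7%, 94.7% and 90.4% (k-means) for K = 2, 3 and 4. The classifier succeeds at every K tried although there is nothing to find.

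**Step 2: one group cannot be assessed.** Deviance per subject is D = −(2/n) Σ log p, where p is the predicted probability of the subject's own label. With one class, p = 1 and D = 0 whatever the data, so K = 1 cannot be compared with K = 2 or more.

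**Step 3: comparing K by deviance.** For equal-sized groups the null deviance per subject is 2 ln K: 1.39, 2.20, 2.77 and 3.22 for K = 2 to 5. Residual deviance is (1 − share explained) × 2 ln K. At n = 200 with independent variables (equal sizes are an approximation):

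- k-means, shares 0.83, 0.80, 0.74, 0.72: residuals 0.24, 0.44, 0.72, 0.90.
- Ward, shares 0.40, 0.46, 0.48, 0.51: residuals 0.83, 1.19, 1.44, 1.58.

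Minimum deviance points to K = 2 in both, even for Ward, where the share explained rises with K. With four true groups simulated, minimum deviance chose K = 2 in 9 of 12 data sets (6 of 6 Ward, 3 of 6 k-means) and, in a separate run, in 10 of 12.

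**Step 4: would the listed model-based clustering protect the plan?** A Gaussian mixture with shared diagonal covariance was fitted for K = 1 to 5 and judged by BIC, with no groups present. It chose K = 1 in 24 of 24 data sets with independent variables, but K = 3 to 5 in 24 of 24 with correlated variables.

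**Step 5: the comparison with cohort.** In one homogeneous correlated population with random cohort labels and Ward clusters (K = 2 to 4), the chi-square test of cluster by cohort rejected in 4.4–6.0% of 1,000 data sets per setting (n = 300, 46 variables) and 4.9–5.6% (n = 200, 40 variables). That is close to the nominal 5%.

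**The case against.** The strongest reply is that the text does not say outright that the lasso chooses the number of groups. It lists four tools in one sentence, ties 10-fold cross-validation expressly only to the penalty weight, and calls its main approach model-based clustering, which can return one group. The sources cited for the method may name a criterion, but they are not in the supplied reference list, and a later analysis plan may add one. This stands as a limit: the lasso reading is the most direct one, not the only one. It does not remove the gap. No criterion or one-group option is written for the mixture route either, and Step 4 shows that BIC alone is no safeguard when variables are correlated, as measurements on the same person can be expected to be.

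A reader might infer that the plan will always report pheno-groups. The documents do not support that, because the mixture route could return one. Finding two or more groups in every simulated data set is no evidence for it when only K = 2 and above were offered.

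A reader might also infer that the Aim 1d association test is invalid. Step 5 shows otherwise: cohort is an external label, and a partition of a continuum can be compared fairly across cohorts.

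Nor does the plan say that lasso accuracy will be presented as validation; its stated use is classification with few variables. Finally, this is one aim among several and not the primary IL-6 comparison.

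**Conclusion.** The concern holds on the most direct reading of Section 13.3. The cross-validation described there cannot show that pheno-groups exist or how many there are. It reached accuracies of about 0.67 to 0.97 in homogeneous data and has no way to assess one group. The tendency towards too few groups is secondary: it rests on small runs, an assumed group separation, and minimum deviance as the criterion, which the plan does not state.

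What would be unsupported is the description of pheno-groups as discrete types, not the comparison of a given partition between cohorts. The sizes depend on assumed sample sizes, variable counts and correlation structures. Recovery was well above the largest-class rate in every no-group setting in Step 1. The point should be corrected before analysis.

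**What to change.** In Section 13.3 or the analysis plan:

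1. State that cross-validated lasso performance will not be used to choose or validate the number of pheno-groups. Keep the lasso only for simplified assignment.
2. Choose the number from the clustering itself, with one group as a candidate. Judge it against a single-population reference with the observed covariance (gap statistic or parametric bootstrap) over the full range of K, and require split-half re-clustering agreement. Do not rely on BIC alone.
3. If one group is not rejected, report the groups as a descriptive partition of a continuum and relate the principal components to cohort.

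The cost is wording and modest computing time. Power is limited when groups overlap: a bootstrap test of the two-cluster index rejected one group in 0 of 60 data sets with no groups, 98% with two true groups and only 42% with four. Non-rejection is therefore not proof of no groups. That simulation used the two-cluster index only; the full-range version was not simulated and should be checked on simulated data before it is fixed in the plan. The sponsor must also accept that the answer may be that no discrete pheno-groups were found.
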